#### 15.2. SECONDARY EFFICACY ENDPOINTS

#### BORR

BORR in Parts A, B and C is one of the secondary efficacy endpoints. Both BICR-assessed BORR and Investigator-assessed BORR by RECIST 1.1 or iRECIST in Parts A, B and C will be calculated.

BICR-assessed BORR by iRECIST and investigator-assessed BORR by RECIST 1.1 or iRECIST in Parts B and C will be calculated.

Overall responses evaluated according to iRECIST will be used for analysis. iRECIST defines i-Unconfirmed Progression (iUPD) on the basis of RECIST 1.1 principles; however, iUPD requires confirmation, which is done on the basis of observing either a further increase in size (or in the number of new lesions) in the lesion category in which progression was first identified in (ie, target or non-target disease), or progression (defined by RECIST 1.1) in lesion categories that had not previously met RECIST 1.1 progression criteria. However, if progression is not confirmed, but instead tumour shrinkage occurs (compared with baseline), which meets the criteria of iCR, iPR, or iSD, then the bar is reset so that iUPD needs to occur again (compared with nadir values) and then be confirmed (by further growth) at the next assessment for i-Confirmed Progression (iCPD) to be assigned. If no change in tumour size or extent from iUPD occurs, then the timepoint response would again be iUPD. This approach allows atypical responses, such as delayed responses that occur after pseudo progression, to be identified, further understood, and better characterised. The iBOR is the best time-point response recorded from the start of the study treatment until death or lost to follow up before the end of the study, whichever occurs first, taking into account any requirement for confirmation. Confirmation of iCR and iPR is the same as that in Table 2 per RECIST v1.1. Confirmation of progression is also required per iRECIST.

BORR will be summarized by number of patients and percentages. The BORR and its 95% confidence interval will be presented. The 95% (exact) confidence interval will be calculated

Document: \\ieedc-vnac01\Biosdata\Genexine\GX-188E\GYA02599\Biostatistics\Documentation\SAP

Author: [name] Version Number: 1.1

Version Date: 05Sep2022

Template No: CS\_TP\_BS016 Revision 6 Reference: CS\_WI\_BS005

Analysis Plan Page 31 of 48

based on the Clopper-Pearson method. PROC FREQ procedure of SAS will be used to calculate 95% (exact) confidence interval by the Clopper-Pearson method.

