Time point response after RECIST 1.1 progression	
 
Up to 5 (2 per site) measured (but not included in the SOM of target lesions identified at baseline) and recorded as new lesions target (NL-T) with an i-sum of measurements (iSOM)
 
Other new lesions (measurable/non-measurable) are recorded as new lesions non-target (NL-NT)
 
New lesions do not have to resolve for subsequent iSD or iPR providing that the next assessment did not confirm progression
 
There can be iSD, iPR or iCR after RECIST 1.1 PD
 
First RECIST 1.1 PD is "unconfirmed" for iRECIST – termed iUPD
 
iUPD must be confirmed at the next assessment (4-8 weeks)
 
If confirmed, termed iCPD
 
Time point response is dynamic and based on
 
Change from baseline (for iCR, iPR, iSD) or change from nadir (for PD)
 

Confirmation of progression required	• The last i-response  First RECIST 1.1 PD is "unconfirmed" for iRECIST; disease progression must be confirmed at the next
	assessment (4-8 weeks later
	Treatment past RECIST 1.1 PD is permitted if patient clinically stable  • No worsening of performance status  • No clinically relevant ↑ in disease related symptoms  • No requirement for intensified management of disease related symptoms (analgesics, radiation, palliative care)
Collection of reason why progression cannot be confirmed	Record the reason iUPD not confirmed
cannot be confirmed	Not stable     Treatment stanged but notice t not
	
 
Treatment stopped but patient not reassessed/imaging not performed
 

	iCPD never occurs
	Patient has died

Assessment at Screening and Prior to RECIST 1.1 Progression

Until radiographic disease progression based on RECIST 1.1, there is no distinct iRECIST assessment.

Assessment and Decision at RECIST 1.1 Progression

For participants who show evidence of radiological PD by RECIST 1.1 as determined by the Investigator, the Investigator will decide whether to continue a participant on study treatment

until repeat imaging is obtained (using iRECIST for participant management (see Table 6 and Figure 5). This decision by the Investigator should be based on the participant's overall clinical condition.

Clinical stability is defined as the following:

- Absence of symptoms and signs indicating clinically significant progression of disease
- No decline in ECOG performance status

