# Confirmation of Progression

Progression is considered confirmed, and the overall response will be iCPD, if ANY of the following occurs:

- Any of the factors that were the basis for the initial iUPD show worsening
  - o For target lesions, worsening is a further increase in the sum of diameters of ≥5 mm, compared to any prior iUPD time point
  - For non-target lesions, worsening is any significant growth in lesions overall, compared to a prior iUPD time point; this does not have to meet the "unequivocal" standard of RECIST 1.1
  - o For new lesions, worsening is any of these:
    - An increase in the new lesion sum of diameters by ≥5 mm from a prior iUPD time point
    - Visible growth of new non-target lesions
    - The appearance of additional new lesions
- Any new factor appears that would have triggered PD by RECIST 1.1

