### Persistent iUPD

Progression is considered not confirmed, and the overall response remains iUPD, if:

- None of the progression-confirming factors identified above occurs AND
- The target lesion sum of diameters (initial target lesions) remains above the initial PD threshold (by RECIST 1.1)

Additional imaging for confirmation should be scheduled 4 to 8 weeks from the imaging on which iUPD is seen. This may correspond to the next visit in the original visit schedule. The assessment of the subsequent confirmation imaging proceeds in an identical manner, with possible outcomes of iCPD, iUPD, and iSD/iPR/iCR.

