## Resolution of iUPD

Progression is considered not confirmed, and the overall response becomes iSD/iPR/iCR, if:

- None of the progression-confirming factors identified above occurs, AND
- The target lesion sum of diameters (initial target lesions) is not above the initial PD threshold.

The response is classified as iSD or iPR (depending on the sum of diameters of the target lesions), or iCR if all lesions resolve.

In this case, the initial iUPD is considered to be pseudo-progression, and the level of suspicion for progression is "reset". This means that the next visit that shows radiographic progression, whenever it occurs, is again classified as iUPD by iRECIST, and the confirmation process is repeated before a response of iCPD can be assigned.

Management Following the Confirmatory Imaging

If repeat imaging does not confirm PD per iRECIST, as assessed by the Investigator, and the participant continues to be clinically stable, study treatment may continue and follow the regular imaging schedule. If PD is confirmed, participants will be discontinued from study treatment.

NOTE: If a participant has confirmed radiographic progression (iCPD) as defined above, but the participant is achieving a clinically meaningful benefit, an exception to continue study treatment may be considered following consultation with the Sponsor. In this case, if study treatment is continued, tumor imaging should continue to be performed following the intervals as outlined in the Schedule of Events (Appendix 1) and submitted to the central imaging vendor.

Detection of Progression at Visits After Pseudo-progression Resolves

After resolution of pseudo-progression (i.e., achievement of iSD/iPR/iCR), iUPD is indicated by any of the following events:

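### SAP 15.2 keeps an unchanged scan after iUPD as iUPD, whereas protocol Appendix 6 can make the same scan iSD, so a patient's iRECIST disease-control status can depend on which text is followed

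*SAP*

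**What the plan says.** SAP 15.2, under BORR, describes what follows an unconfirmed progression (iUPD) in two sentences. On reset, it covers the patient whose repeat scan does not establish progression: "but instead tumour shrinkage occurs (compared with baseline), which meets the criteria of iCR, iPR, or iSD, then the bar is reset". On a static scan it says: "If no change in tumour size or extent from iUPD occurs, then the timepoint response would again be iUPD". Neither sentence mentions the PD threshold for target lesions or what triggered the iUPD. The same paragraph then defines iBOR as the best time-point response, subject to confirmation.

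Protocol Appendix 6 sorts the repeat scan differently:

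- Confirmation of Progression requires worsening ("Any of the factors that were the basis for the initial iUPD show worsening") or a new factor that would itself be PD.
- Persistent iUPD requires that no confirming factor occurs and also that "The target lesion sum of diameters (initial target lesions) remains above the initial PD threshold (by RECIST 1.1").
- Resolution of iUPD requires that no confirming factor occurs and that "The target lesion sum of diameters (initial target lesions) is not above the initial PD threshold". Then: "The response is classified as iSD or iPR (depending on the sum of diameters of the target lesions), or iCR if all lesions resolve". The episode is treated as pseudo-progression and the process starts afresh.
- The Appendix 6 table, on new lesions: "New lesions do not have to resolve for subsequent iSD or iPR providing that the next assessment did not confirm progression".

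Appendix 6 also assigns iUPD at the first RECIST 1.1 progression whatever its cause, so new or non-target lesions alone can trigger it.

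SAP 15.2 plans BORR and DCR by iRECIST for both BICR and investigator in Parts A, B and C, and ORR24 by iRECIST in Part A. SAP 3.3, which lists departures from the protocol, does not mention this rule.

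**The concern.** After an iUPD, Appendix 6 looks at the target-lesion sum against the PD threshold, while the SAP looks at change since the iUPD scan and at shrinkage from baseline. These tests are not equivalent. A scan on which nothing has moved can pass the Appendix 6 test for resolution and still be iUPD under the SAP.

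DCR counts CR, PR and SD; iUPD does not count. The category given to such a scan can therefore decide whether a patient is disease-controlled by iRECIST. The reset matters as well: after an Appendix 6 resolution, later growth is a new iUPD that needs its own confirmation, whereas if iUPD has persisted, the same growth would confirm progression.

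The documents do not say which text binds the BICR iRECIST reads or any programmed derivation.

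**Working it through.** The plan has no stated figure that depends on this rule, so the check applies both texts to the same scans.

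**Inputs.** PD threshold: at least 20% and at least 5 mm above the smallest sum on study. PR: at least 30% below baseline (protocol 22.2 and Appendix 5). Assumed baseline target sum: 60 mm, so the PR limit is 0.70 × 60 = 42 mm. If the sum never falls below baseline, the PD threshold is 1.20 × 60 = 72 mm, a rise of 12 mm, which exceeds 5 mm. In every row the repeat scan is unchanged from the iUPD scan, so no confirming factor is present.

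| Trigger of iUPD | Target sum | Appendix 6 | SAP no-change sentence | SAP shrinkage sentence | Result |
|---|---|---|---|---|---|
| Target lesions | 78 mm (+30%) | 78 ≥ 72: iUPD | iUPD | does not apply | agree |
| New lesion | 60 mm (0%) | 60 < 72: iSD, reset | iUPD | does not apply | conflict |
| New or non-target | 66 mm (+10%) | 66 < 72: iSD, reset | iUPD | does not apply | conflict |
| New lesion | 54 mm (−10%) | below threshold: iSD, reset | iUPD | iSD, reset | SAP ambiguous |
| New or non-target | 38 mm (−36.7%) | 38 ≤ 42: iPR, reset | iUPD | iPR, reset | SAP ambiguous |

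In the last two rows the smallest sum is the current one, so the threshold is 1.20 × 54 = 64.8 mm and 1.20 × 38 = 45.6 mm; neither sum reaches it.

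**The clear case.** Take the second row. The first on-study scan is at about 9 weeks (protocol 22.1.2; Week 10 in the schedule). The target sum is 60 mm at baseline and stays there; a new lesion appears at Week 10 and does not change afterwards. Week 10 is iUPD under both texts. On the repeat scan Appendix 6 gives iSD and the SAP gives iUPD. Because Week 10 was her first on-study assessment, she has no earlier iSD to count. If later scans are also unchanged, Appendix 6 continues to give iSD, and she can count in iRECIST DCR subject to the SD confirmation and duration rules. Under the SAP sentence she cannot.

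**Does another Appendix 6 rule remove the conflict?** Its closing exception stops iUPD from resolving when the new-lesion burden has risen from its smallest value at a later episode. It does not cover an unchanged scan at the first episode.

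**Size per patient.** 1/60 = 1.7 percentage points. For illustration only, 22/60 = 36.7% (95% Clopper-Pearson 24.6 to 50.1) becomes 23/60 = 38.3% (26.1 to 51.8).

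**The case against.** The strongest reply is that the SAP paragraph is background on iRECIST and not a derivation rule. It opens by saying that responses evaluated by iRECIST will be used. SAP 5.4 refers to an overall-response CRF page covering RECIST and iRECIST, and SAP 15 sends the investigator to Appendix 6 for confirming progression. On that view the time-point categories arrive already assigned under Appendix 6, and the SAP only derives iBOR from them.

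This stands in part: investigator data may well follow Appendix 6 already. It does not remove the conflict. The paragraph leads directly into the iBOR definition, it is the SAP's only written time-point rule after iUPD, and nothing says which text governs the BICR reads.

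Four stronger readings are tempting, but the documents do not support them:

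- A reader might infer that the texts disagree for every patient whose progression came from new or non-target lesions and then held steady. They do not clearly do so: when the target sum has fallen, the shrinkage sentence ("but instead tumour shrinkage occurs (compared with baseline), which meets the criteria of iCR, iPR, or iSD") can give the same answer as Appendix 6.
- For the same reason, the case of 60 to 38 mm with an unchanged new lesion does not prove a shift in BORR. It shows that two SAP sentences point to different answers.
- A sum of 60, then 74 (iUPD), then 68 mm may look like a further conflict. Appendix 6 gives iSD because 68 is below 72. The scan has changed, so the no-change sentence does not apply, and the sum has not shrunk from baseline. The SAP is silent on it; it does not assign iUPD.
- A reader might expect a distorted comparison of BICR with investigator. The concordance summary in SAP 15 is in the paragraph on RECIST 1.1 assessments; no iRECIST concordance analysis is specified.

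Also, not every affected scan changes a result. A patient with a qualifying iSD, iPR or iCR at another time is disease-controlled under either text, and clinically unstable patients need no repeat scan.

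**Conclusion.** The point holds in a limited form. SAP 15.2 and Appendix 6 clearly disagree when three conditions coincide: iUPD was triggered by new or non-target lesions, the target sum is neither below baseline nor above the PD threshold, and the repeat scan is unchanged. The consequence is a possible change in iRECIST DCR status for a patient with no other qualifying response, subject to the SD confirmation and duration rules.

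Where the target sum has shrunk from baseline, the SAP contradicts itself. That leaves iRECIST BORR, and iRECIST ORR24 in Part A, ambiguous, without a demonstrated conflict with the protocol.

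The effect is 1.7 points per reclassified patient in a 60-patient rate. No total can be given, because the documents say nothing about how often progression comes from new or non-target lesions alone or how often it is then static.

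The primary endpoint (BICR ORR24 by RECIST 1.1) and the RECIST 1.1 analyses of PFS and DOR are unaffected. This is a correction to secondary iRECIST summaries, worth making before database lock because it is cheap and removes a choice that could otherwise be made after the data are seen.

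**What to change.** Reconcile SAP 15.2 with Appendix 6. Replace the reset sentence and the no-change sentence with one statement: iRECIST time-point responses, for both investigator and BICR, follow protocol Appendix 6, including its exception for an increased new-lesion burden at later episodes. State that iBOR, BORR, DCR and the Part A iRECIST ORR24 are derived from those responses, and check that the instructions for the BICR iRECIST reads name the same rule.

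Appendix 6 itself should not be altered for this purpose. It also governs whether treatment continues after progression, so changing it would not be a purely statistical edit.

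The cost is SAP wording and, if needed, a clarification to the central reader. It needs no new data, scans or patients.

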#### ORR24

24 weeks ORR in Part A is one of the secondary efficacy endpoints. Both BICR-assessed ORR24 and Investigator-assessed ORR24 by RECIST 1.1 or iRECIST in Part A will be calculated.

 $ORR_{24}$  will be summarized by number of patients and percentages. The  $ORR_{24}$  and its 95% confidence interval will be presented. The 95% (exact) confidence interval will be calculated based on the Clopper-Pearson method.

#### DCR

DCR is defined as the percentage of patients who had a CR, PR or Stable Disease. 95% confidence interval of DCR will be calculated using the Clopper-Pearson method.

DCR in Parts A, B and C is one of the secondary efficacy endpoints. Both BICR-assessed DCR and Investigator-assessed DCR by RECIST 1.1 or iRECIST in Parts A, B and C will be calculated.

#### DOR

Duration of response only applies to the subgroup of patients in efficacy evaluation population whose best overall response is CR or PR according to RECIST v1.1. Median DOR time is the timepoint at which the probability of disease progression equals 50% after documented objective tumor response (PR or CR).

Subject continuing without disease progression or death will be censored and the censoring date will be the date of the last evaluable tumor assessment prior to data cut-off/start of subsequent anti-cancer therapy. In case of progression or death after two or more consecutive missed tumor assessments, censoring will be done at last evaluable tumor assessment date prior to the missed tumor assessments. Reason of censoring will be summarized.

The Kaplan-Meier method will be used to estimate the median DOR time, and 2-sided 95% Cl for the median will be provided. BICR-assessed DOR and investigator-assessed DOR by RECIST v1.1 will be displayed for Part A, Part B and Part C. Kaplan-Meier curve for BICR-assessed DOR will be presented.

#### TTR

TTR is time from treatment initiation to the best objective response achieved (i.e., PR or CR whichever occurs earlier). This endpoint is only determined for patients who have a PR or CR by RECIST v1.1. Median TTR is the timepoint from treatment initiation to the best objective response achieved in 50% of patients. Median TTR will be calculated using descriptive statistics

Document: \\ieedc-vnac01\Biosdata\Genexine\GX-188E\GYA02599\Biostatistics\Documentation\SAP

Author: [name] Version Number: 1.1

Version Date: 05Sep2022

Template No: CS\_TP\_BS016 Revision 6 Reference: CS\_WI\_BS005

PROTOCOL GX-188E-005

Analysis Plan Page 32 of 48

in efficacy evaluation population restricted to patients with the best objective response. BICR-assessed TTR and investigator-assessed TTR by RECIST v1.1 will be displayed for Part A, Part B and Part C.

#### PFS

PFS is defined as the time from treatment initiation until documented disease progression or death from any cause. If the patient progresses or dies after two or more consecutive missed tumor assessment visits, the patient will be censored at the time of the latest evaluable RECIST v1.1 assessment. Two consecutive missed/non-evaluable tumor assessment visits is defined as no evaluable tumor assessment within 126 days (2\*9 weeks) of first dose or the previous evaluable RECIST 1.1 measurement. If the patient has no evaluable tumor assessment visits after first dose or does not have evaluable baseline tumor assessment data, the patient will be censored on the date of first dose. Table 3 defines the censoring rules for PFS.

Table 3. Censoring Rules for Analysis of Progression-Free Survival

Description	Event/Cen sor	Date of Event/Censor
Documented progression before two consecutive missed tumor assessment visits	Event	Date of documented disease progression
Death (without progression) before two consecutive missed tumor assessment	Event	Date of death
Death or progression after two or more consecutive missed tumor assessments	Censor	Date of last evaluable tumor assessment prior to the consecutive missed tumor assessment visits
Progression or death after subsequent anti-cancer therapy	Censor	Date of the last evaluable tumor assessment prior to start of subsequent anti-cancer therapy
No evaluable baseline or post- baseline tumor assessment	Censor	Date of first dosing of study medication

Document: \(\)\ieedc-vnac01\\Biosdata\\Genexine\\GX-188E\\GYA02599\\Biostatistics\\Documentation\\SAP\)

Author: [name] Version Number: 1.1

Version Date: 05Sep2022

Template No: CS\_TP\_BS016 Revision 6 Reference: CS\_WI\_BS005

PROTOCOL GX-188E-005

Analysis Plan Page 33 of 48

No progression and no death before	Censor	Date of last evaluable tumor
end of study or data cut-off		assessment

Median PFS time (months) is the timepoint at which the probability of progression-free survival equals 50% in the efficacy evaluable population.

6-month PFS rate is the proportion of efficacy evaluable patients without evidence of disease progression and who are alive 6 months after treatment initiation.

Kaplan-Meier method will be used to estimate median PFS and the corresponding 95% CI. Kaplan-Meier curves will be constructed to provide a visual presentation of the BICR assessed PFS rate change with time. The PFS rate and 95% CI at 6 months will also be summarized.

BICR-assessed PFS and investigator-assessed PFS by RECIST v1.1 will be displayed for Part A, Part B and Part C.

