#### 5.4. EFFICACY EVALUABLE POPULATION

All patients who complete the study will be included into the efficacy evaluable population. These patients will be identified by using the "Subject's status?" with answer "Completed trial" from end of study page of CRF.

All patients who discontinue the study treatment regimen early due to treatment-related toxicity will be considered evaluable for efficacy. These patients will be identified as those with DLT. Patients who discontinue study due to disease-related death, unequivocal tumor progression or with at least 1 post-baseline tumor assessment must have received at least 45 days on protocol treatment to be considered evaluable for efficacy. Patients who discontinue study due to disease-related death will be identified by using the "Primary reason for premature discontinuation from study" with answer "Death" from end of study page of CRF and the "Was death disease related" with answer "Yes" from death details page of CRF. Patients who discontinue study due to unequivocal tumor progression will be identified by using "Primary reason for premature discontinuation from study" with answer "Disease Relapse or Progression" from end of study page of CRF. Patients who discontinue study with at least 1 post-baseline tumor assessment will be identified as those with at least one RECIST/iRECIST Overall Response data on RECIST/iRECIST Overall Response page of CRF after screening visit. Patients in Part B and Part C who do not meet the aforementioned requirements will be considered non-evaluable for response and may be replaced. Patients from Part A, who receive the recommended Phase 2 regimen and who meet the aforementioned criteria for the Efficacy Evaluable Population will be included in the analysis for Part B and Part C. The following table provides further, more specific details.

Document: \\ieedc-vnac01\Biosdata\Genexine\GX-188E\GYA02599\Biostatistics\Documentation\SAP

Author: [name] Version Number: 1.1

Version Date: 05Sep2022

Template No: CS\_TP\_BS016 Revision 6 Reference: CS\_WI\_BS005

Analysis Plan Page 16 of 48

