### 6. GENERAL CONSIDERATIONS

#### 6.1. REFERENCE START DATE AND STUDY DAY

Study Day will be calculated from the reference start date and will be used to show start/ stop day of assessments and events.

Reference start date is defined as the day of the first dose of study medication (either GX-188E or P, whichever occurred first), Day 1 is the day of the first dose of study medication and will appear in every listing where an assessment date or event date appears.

- If the date of the event is on or after the reference date, then:
  - Study Day = (date of event reference date) + 1.
- If the date of the event is prior to the reference date, then:
  - Study Day = (date of event reference date).

In the situation where the event date is partial or missing, study day, and any corresponding durations will appear partial or missing in the listings.

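### SAP 15.2 PFS: an early death with no post-dose scan is both an event and censored, and the 126-day limit can count one missed scan as two

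*SAP*

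**What the plan says.** The PFS text of SAP 15.2 begins: "PFS is defined as the time from treatment initiation until documented disease progression or death from any cause". Table 3 then sets the event and censoring rules. Three rows matter here:

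- Row 2, "Death (without progression) before two consecutive missed tumor assessment", is an event on the date of death.
- Row 3 censors progression or death after two or more consecutive missed assessments. Its date is "Date of last evaluable tumor assessment prior to the consecutive missed tumor assessment visits".
- Row 5, "No evaluable baseline or post- baseline tumor assessment", is censored on the date of first dosing. The prose agrees: "no evaluable tumor assessment visits after first dose or does not have evaluable baseline tumor assessment data, the patient will be censored" on that date. Neither place makes an exception for death.

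The limit that separates rows 2 and 3 is in the prose: "Two consecutive missed/non-evaluable tumor assessment visits is defined as no evaluable tumor assessment within 126 days". The count starts at first dose or at the previous evaluable measurement, and the SAP explains it as 2*9 weeks.

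Protocol 22.1.2 and Appendix 1 schedule scans at Week 10 and Week 19 (±3 days each), then every 9 weeks (±7 days), by calendar date. Protocol 24.5 also counts death as a PFS event and gives no censoring rules.

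PFS is estimated in the efficacy evaluable population. Under SAP 5.4, patients who leave through disease-related death or progression, or with at least one post-baseline assessment, "must have received at least 45 days on protocol treatment to be considered evaluable for efficacy". Patients who stop for a DLT are included whatever their time on treatment.

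**The concern.** The first problem is a contradiction. Because the missed-scan count can start at first dose, row 2 reaches patients who have never had a post-dose scan. Row 5 reaches the same patients and gives the opposite answer. Two programmers could follow the SAP faithfully and code one death differently. Censoring it also fits badly with the SAP's own 6-month PFS rate, which requires the patient to be alive at 6 months.

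The second problem is the limit. On a 9-week schedule, the scan that follows one missed scan is due 18 weeks after the previous one, which is 126 days. The limit therefore sits on the nominal gap for one miss and leaves no room for the visit windows. A scan done late but in window can turn one missed assessment into two, and the progression it shows is then censored.

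At stake are median PFS, the 6-month PFS rate and the Kaplan-Meier curves. DOR has the same rule on two or more missed assessments but no day count of its own.

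**Working it through.** **The plan's figure.** 2 × 9 weeks × 7 days = 126 days. It reproduces exactly.

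**Death without a post-dose scan.** Take a patient with an evaluable baseline and no later anti-cancer therapy, who dies on Day 50 before the first scan. Under the PFS definition and row 2 this is an event at Day 50. Under row 5 and the prose it is censoring at Day 1. The conflict runs to 126 days after first dose; beyond that, an unscanned death is censored on either route.

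**How often this can arise.** The SAP does not say how days on protocol treatment are counted. If its exposure formula (SAP 13.1: last dose − first dose + 1) is used:

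- An on-time Week 7 dose is 42 days after first dose, so 42 + 1 = 43 days. That is below 45, and the patient is excluded.
- With the ±3-day window the count is 40 to 46 days, so only a Week 7 dose given 2 or 3 days late reaches 45.
- The next dose is at Week 10, where the protocol lists the scan before pembrolizumab.

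What remains is mainly late Week 7 dosing, a missed or non-evaluable Week 10 scan, and patients who stop for a DLT and die unscanned.

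**Gaps after exactly one missed scan.** Scan days, elapsed from first dose: Week 10 = 63 ± 3, Week 19 = 126 ± 3, Week 28 = 189 ± 7, Week 37 = 252 ± 7, Week 46 = 315 ± 7. All scans are in window.

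| From → to | Shortest | Nominal | Longest | Day combinations over 126 |
|---|---|---|---|---|
| First dose → Week 19 | 123 | 126 | 129 | 3 of 7 |
| Week 10 → 28, or Week 19 → 37 | 116 | 126 | 136 | 49 of 105 |
| Week 28 → 46 | 112 | 126 | 140 | 105 of 225 |

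The last column counts possible days, not expected frequencies. A gap of exactly 126 days is still within the limit. The clearest failure is a missed Week 10 scan with progression found 127 to 129 days after first dose.

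**Effect on 6-month PFS.** Assumptions: N = 60, 21 patients progression-free at 6 months, no other censoring.

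- Correctly coded: 21/60 = 35.0%. SE = √(0.35 × 0.65/60) = 6.16%; 95% half-width = 1.96 × 6.16 = 12.1 points.
- With 1, 2 or 3 of the failures censored at first dose: 21/59 = 35.6%, 21/58 = 36.2%, 21/57 = 36.8%.

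These figures apply to censoring at first dose. With a Week 10 scan as the starting point, a gap over 126 days puts the progression at day 187 or later (60 + 127), after 6 months (6 × 30.4375 = 182.6 days). There the curve is raised only from the lost progression onward, and the 6-month rate is not raised.

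**The case against.** The best defence is that little turns on this. PFS is a descriptive secondary endpoint with no test. The 45-day rule may remove most deaths before Week 10. Protocol 22.1.3 asks for imaging at treatment discontinuation. Confirmatory scans about 4 weeks after response, stable disease or progression shorten many later gaps: with a confirmatory scan at about day 91 (63 + 28), missing Week 19 leaves only 91 to 105 days to Week 28. Overall survival, including its 6-month rate, counts every death in the same population. All of this stands and limits the size. None of it says which Table 3 row governs, or makes 126 days the right limit for two missed scans.

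Three stronger readings are tempting, and the documents do not support them.

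- A reader might infer from SAP 6.1, where "Day 1 is the day of the first dose of study medication", that an on-time Week 19 scan falls on Study Day 127 and is already outside the limit. But the same 126 days also runs from a previous scan and is explained as 2*9 weeks. That fits only elapsed days, and an on-time scan is then inside.
- A reader might infer that every early death is exposed to the conflict. The 45-day requirement is on treatment, not survival, so many such patients may not be in the analysis at all.
- A reader might expect that adding PFS to the safety-population sensitivity analysis would reveal the problem. It would use the same censoring rules and so would not test them.

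**Conclusion.** Wrong as written, and minor. The SAP gives two answers for one definable death, and its missed-scan limit censors some progressions that follow a single missed scan. Both defects follow from the text and the visit schedule without assumptions. Where the patient is censored, the error favours the treatment: the PFS curve is too high from the lost event onward.

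The size does rest on assumptions. With N = 60 and a true 6-month PFS of 35%, each patient wrongly censored at first dose adds about 0.6 points, small beside a 95% half-width of about 12. The documents do not allow the number of such patients to be estimated. ORR24 is unaffected.

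**What to change.** Amend SAP 15.2 before database lock:

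1. **Precedence.** In the prose and Table 3 row 5: censor at first dose, unless the patient dies before two consecutive scheduled assessments are missed and before subsequent anti-cancer therapy, in which case death is an event on the date of death.
2. **Missed assessments.** Replace the 126-day count. Two missed means that two consecutive scheduled windows (Week 10 and Week 19 ±3 days, then every 9 weeks ±7 days) have both closed with no evaluable scan since the last evaluable scan of any kind, confirmatory and unscheduled scans included. A scheduled scan that the protocol allows to be skipped after a confirmatory scan does not count as missed.
3. **Censoring date.** State that when no evaluable post-dose scan precedes the missed assessments, the date is first dose. Read literally, row 3 points to the baseline scan, which is taken before treatment starts.
4. **DOR.** Refer its rule to the same definition.

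Simply lengthening the day limit would not work. After a confirmatory scan on day 91, the Week 19 and Week 28 windows have both closed by day 196 (189 + 7), a gap of 105 days, which is already shorter than 126.

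The cost is a few sentences and visit-window logic in the program. PFS may come out slightly less favourable.
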